4.4.3. Supportive Secondary Endpoints

Unless otherwise specified, all supportive/other secondary efficacy analyses will be guided by the “efficacy” estimand and will be conducted using the EAS. Missing data will be handled using an MMRM.

Table GPIF.4.3. Secondary Measures Not Controlled for Type 1 Error

| Objective – Demonstrate Superiority of Tirzepatide MTD to Placebo for: | Endpoint | Analytical Approaches |
|--|--|---|
| Change in excessive daytime sleepiness | Change in ESS score from baseline to Week 52 | MMRM analysis described in Section 4.4.1.1 will be conducted. |

| Objective – Demonstrate Superiority of Tirzepatide MTD to Placebo for: | Endpoint | Analytical Approaches |
|---|---|---|
| Change in patient-reported functional status as assessed by FOSQ (10 items) | Change in FOSQ-10 total score from baseline to Week 52 | MMRM analysis described in Section 4.4.1.1 will be conducted. |
| Change in patient-reported functional status as assessed by FOSQ (30 items) | Change in FOSQ (30 item) total score and all functional domain scores from baseline to Week 52 | MMRM analysis described in Section 4.4.1.1 will be conducted. |
| Change in Body Weight | Percent of participants who achieve $\geq 10\%$, $\geq 15\%$, and $\geq 20\%$ body weight reduction. | Logistic models described in Section 4.4.1.1 with the following covariates: treatment, geographic region (US/OUS), baseline AHI (not severe/severe), gender, and baseline bodyweight as a covariate. |
| Change in Lipid Parameters | Change in: HDL-cholesterol non-HDL-cholesterol triglycerides | MMRM analysis described in Section 4.4.1.1 will be conducted. |
| Hierarchical assessment of PRO change | A hierarchical combination of the following: o Change in PROMIS Sleep-related impairment short form 8a o Change in PROMIS Sleep disturbance short form 8b | Win ratio analysis described in Section 4.4.3.1 will be conducted. |
| Change in supportive secondary PROs | Summary of item 8 of PROMIS Sleep Disturbance short form 8b | Counts and percentages of participants at each time point will be summarized by nominal visit and by treatment. A shift table from baseline to postbaseline will be created at each postbaseline visit. |
| | Change in: SF-36v2 acute form domain scores From baseline to Week 52 | MMRM analysis of T-score described in Section 4.4.1.1 will be conducted. Description of T-score calculation provided in Sections 4.7.2.4 and 4.7.2.5. |
| | Percent of participants with improved categorical shift in: PGIS-OSA Sleepiness PGIS-OSA Fatigue PGIS-OSA Snoring From baseline to Week 52 | For each question, the proportion of participants with improvements from baseline will be summarized. Shift analysis from baseline to Week 52 will also be performed. |
| | Proportion of participants who achieve: $\leq -x$ change in PROMIS Sleep-related impairment $\leq -y$ change in PROMIS Sleep disturbance | Logistic models described in Section 4.4.1.1 with the following covariates: treatment, geographic region (US/OUS) baseline AHI (not severe/severe), gender, and baseline score as a covariate. |

| Objective – Demonstrate Superiority of Tirzepatide MTD to Placebo for: | Endpoint | Analytical Approaches |
|--|---|---|
| | From baseline to Week 52 (x and y will be derived from blinded interim analysis) | |
| Change in Insulin | Change in fasting insulin from baseline to Week 52 | MMRM analysis described in Section 4.4.1.1 will be conducted. |
| Change in DBP | Change in DBP from baseline to Week 48 | MMRM analysis described in Section 4.4.1.1 will be conducted. |

Abbreviations: AHI = Apnea-Hypopnea Index; DBP = diastolic blood pressure; ESS = Epworth Sleepiness Scale; FOSQ = Functional Outcomes of Sleep Questionnaire; HDL = high-density lipoprotein; MMRM = mixed model repeated measures; MTD = maximum tolerated dose; PGIS-OSA = Patient Global Impression of Status Obstructive Sleep Apnea; PRO = patient-reported outcome; PROMIS = Patient-Reported Outcomes Measurement Information System; SF-36v2 = Short-Form 36 version 2.

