Statistical treatment comparisons will be performed between tirzepatide MTD and placebo. Unless otherwise noted, all tests of treatment effects will be conducted at a 2-sided alpha level of 0.05, and the confidence interval will be calculated at a 2-sided 95% level. In statistical summaries and analyses, participants will be analyzed as randomized. Analysis models will use geographic region (US/OUS) as a covariate when applicable.

Analysis of covariance will be used to analyze continuous variables collected only at baseline and endpoint. Unless otherwise specified, the model will include treatment and strata (geographic region [US/OUS], AHI stratum [not severe (AHI <30), severe (AHI \geq 30)], and gender) as fixed effects and baseline as a covariate.

MMRMs will be used to analyze continuous variables collected at baseline and more than 1 postbaseline visit. For the MMRM analysis, REML will be used to obtain model parameter estimates for continuous longitudinal variables. All the longitudinal observations at each scheduled postbaseline visit will be included in the analysis. The model will include the fixed class effects of treatment, strata (geographic region [US/OUS] and gender), visit, and treatment-by-visit interaction, as well as the continuous, fixed covariate of baseline value. For analyses of variables other than AHI, the AHI stratum will also be included in the model. Significance tests will be based on least squares means and Type III tests.

For continuous measures, summary statistics may include sample size, mean, standard deviation, median, minimum, and maximum for both the actual and the change from baseline measurements. Least-square means and standard errors derived from the analysis models will also be displayed for the change from baseline measurements. Treatment comparisons will be displayed showing the treatment difference least-square means and the 95% confidence intervals for the treatment differences, along with the p-values for the treatment comparisons.

For categorical measures, summary statistics may include sample size, frequency, and percentages. Fisher's exact test or Pearson's chi-square test will be used for treatment comparisons unless otherwise specified.

Not all analyses described in this SAP will necessarily be included in the CSRs. Any analysis described in this SAP and not provided in the CSR would be available upon request.

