4.1.1. Adjustment for Covariates

The study is stratified by country/geographic region, OSA severity (not severe [AHI <30], severe [AHI \geq 30]), and gender. Unless otherwise specified, the following factors will be adjusted for: geographic region (US/OUS), OSA severity (not severe [AHI <30], severe [AHI \geq 30]), and gender. The value for stratification factors will be obtained from the data collected or derived from the eCRF or PSG results. In addition, the baseline value of the endpoint will be used as a covariate when appropriate.

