4.6.3.9.1. Patient Health Questionnaire

Total scores for the PHQ-9 range from 0 to 27 with total scores categorized as

- none (not depressed): 0 through 4
- mild: 5 through 9
- moderate: 10 through 14
- moderately severe: 15 through 19, and
- severe: 20 through 27.

Shift tables will be provided showing the counts and percentages of participants within each baseline category (maximum value) versus each postbaseline category (maximum value) by treatment.

Additionally, the following 3 outcomes of interest will be compared between treatments (based on the maximum value during baseline and postbaseline):

- any increase in depression category (that is, worsening of depression): includes participants in the none, mild, moderate, or moderately severe category during baseline and with at least 1 postbaseline measurement
- increase from No or Mild Depression to Moderate, Moderately Severe, or Severe Depression: includes participants in the none or mild depression category during baseline and with at least 1 postbaseline measurement, and
- increase from Mild or Moderate Depression to Moderately Severe or Severe Depression: includes participants in the mild or moderate depression category during baseline and with at least 1 postbaseline measurement.

4.6.3.9.2. *Suicidal Ideation and Behavior Solicited Through C-SSRS*

Suicide-related thoughts and behaviors occurring during the entire study period, based on the C-SSRS, will be summarized by treatment group. In particular, for each of the following suicide-related events, the counts and percentages of participants with the event will be summarized by treatment group:

- died by suicide
- nonfatal suicide attempt
- interrupted attempt
- aborted attempt
- preparatory acts or behavior
- active suicidal ideation with specific plan and intent
- active suicidal ideation with some intent to act without specific plan
- active suicidal ideation with any methods (no plan) without intent to act
- nonspecific active suicidal thoughts
- wish to be dead, and
- nonsuicidal, self-injurious behavior.

In addition, the counts and percentages of participants who experienced at least 1 of the composite measures will be presented. The participants with at least 1 postbaseline C-SSRS assessment are included. The composite measure is determined at each assessment by the “yes” or “no” responses in C-SSRS categories by the study participant:

- Category 1 – Wish to be Dead
- Category 2 – Non-specific Active Suicidal Thoughts

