4.7.2.7. Patient Global Impression of Status/Change for OSA Outcomes

The counts and percentages of participants for PGIS for Physical Activity and PGIC response categories at each time point will be summarized by nominal visit and by treatment. A shift table from baseline to postbaseline of 3 PGIS response categories (OSA Sleepiness, Fatigue, and Snoring) and 4 PGIC response categories (OSA Sleepiness, Fatigue, Snoring, and Sleep Quality) will be created at each postbaseline visit.

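### The PGIS-OSA improvement endpoints have no baseline-adjusted treatment comparison, which gives up precision that the collected baseline category would provide

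*SAP*

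**What the plan says.** The objective column of Table GPIF.4.3 (SAP Section 4.4.3) is framed as showing superiority over placebo. For the three PGIS-OSA endpoints the analysis cell reads "For each question, the proportion of participants with improvements from baseline will be summarized", followed by "Shift analysis from baseline to Week 52 will also be performed". SAP Section 4.7.2.7 adds counts by visit and baseline-to-postbaseline shift tables. None of these places gives a model, a covariate, a test, a denominator or a rule for participants who start at the best category.

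The fallback for categorical measures is in SAP Section 4.1: "Fisher's exact test or Pearson's chi-square test will be used for treatment comparisons unless otherwise specified". SAP Section 4.1.1 has a general clause that "the baseline value of the endpoint will be used as a covariate when appropriate", which is not tied to PGIS.

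The two other responder rows of the table are handled differently. Body weight thresholds get a logistic model with baseline body weight. The PROMIS responder row gets one with treatment, region, "baseline AHI (not severe/severe), gender, and baseline score as a covariate".

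Protocol Section 8.1.2.1.6 describes the scales. Fatigue and sleepiness are single 4-point items whose best level means no symptom. Snoring has two items: a 4-point item on how far snoring affects sleep, and a 3-point item on being told by others that one snores.

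**The concern.** Whether someone improves on a 4-point scale depends heavily on where they start. A participant at the best level has no chance of improving, and one at the worst level has three levels to gain. The baseline response is already collected, so this part of the variation can be removed at no extra burden to participants. The default test does not remove it.

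A sizeable group at the best level is plausible. The master protocol's inclusion criteria set AHI and BMI thresholds but no symptom threshold. ISA2 participants have used PAP for at least 3 months, and SAP Section 4.7.3 plans a subgroup with ESS of 10 or less. What is at stake is precision: a real symptom benefit would be estimated with a wider interval than the data allow.

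**Working it through.** **Figures in the plan.** SAP Section 5 gives about 103 per arm in each ISA, 25% dropout and a 2-sided 0.05 level. 103 × 0.75 = 77.25, so 77 to 80 analysed per arm is used below. No power figure is given for PGIS. The related figure with all its inputs stated, at least 90% for percent change in AHI, reproduces: 50 / (50 × √(2/77)) = 6.2, which is power above 0.999. It says nothing about PGIS.

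**Inputs the documents do not give.** These are the share f at the best category at baseline and the improvement probabilities by baseline category. Both are assumptions here.

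**Formulas.** Let w_k be the share in baseline category k, pT_k and pC_k the improvement probabilities, d_k = pT_k − pC_k, d the overall difference and n the number per arm. The variance of the risk difference is V/n, with
- unadjusted: V = pT(1 − pT) + pC(1 − pC)
- adjusted: V = Σ w_k [pT_k(1 − pT_k) + pC_k(1 − pC_k)] + ½ Σ w_k (d_k − d)²

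**Simplest case.** Take f = 0.30, with 50% against 30% improving in every other category (no gradient with severity) and n = 80.
- pT = 0.7 × 0.50 = 0.35; pC = 0.7 × 0.30 = 0.21; d = 0.14
- unadjusted V = 0.35 × 0.65 + 0.21 × 0.79 = 0.3934
- adjusted V = 0.7 × (0.25 + 0.21) + ½ × 0.3 × 0.7 × 0.20² = 0.3220 + 0.0042 = 0.3262
- ratio = 0.3262 / 0.3934 = 0.83
- unadjusted power: 0.14 / √(0.3934/80) = 2.00, giving 0.51
- adjusted power: 0.14 / √(0.3262/80) = 2.19, giving 0.59, a gain of about 8 points

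With f = 0.10 and otherwise the same inputs, V is 0.45 × 0.55 + 0.27 × 0.73 = 0.4446 unadjusted and 0.9 × 0.46 + ½ × 0.1 × 0.9 × 0.20² = 0.4158 adjusted. The ratio is 0.94 and power goes from 0.68 to 0.70, a gain of about 3 points. This is a low case, because only the best category is informative.

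**With a gradient.** Two sets of nine scenarios (f of 10-30%, improvement more likely with greater baseline severity, 80 per arm) gave variance ratios of 0.72-0.90 and 0.70-0.88, with power gains of 4-13 and 6-14 points.

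**Simulation check.** This used a 4-category latent-normal model with correlation 0.5, a treatment shift of 0.5 SD and 77 per arm, 2000 runs per setting.

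| f | Fisher, all | Chi-square, all | CMH by baseline category |
|---|---|---|---|
| 10% | 0.54 | 0.60 | 0.72 |
| 20% | 0.43 | 0.48 | 0.65 |
| 30% | 0.34 | 0.39 | 0.59 |
| 50% | 0.17 | 0.22 | 0.42 |

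Under no treatment effect, chi-square rejected in 4.5-5.7% of runs and CMH in 4.6-6.0%, so both are valid. The gain of CMH over chi-square, 11-20 points, exceeds the analytic range because improvement rises steeply with severity in this model.

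**Does restricting to those who can improve help further?** In the simplest case with f = 0.30, restriction leaves 80 × 0.7 = 56 per arm and a difference of 0.20: 0.20 / √(0.46/56) = 2.21, power 0.60. Adjusting in everyone gave 0.59. The best category contributes no variance once baseline is adjusted for, so leaving it out adds almost nothing. It only changes whom the estimate describes (20 points rather than 14).

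**The case against.** The strongest reply is that the row promises a summary of an uncontrolled endpoint, not a test. The SAP treats comparable single-item outcomes the same way: item 8 of PROMIS Sleep Disturbance and the PGIC scales also get proportions and shift tables. The shift tables show each arm's baseline distribution and improvement from each level. Section 4.1.1 allows baseline adjustment where appropriate, and Section 4.7.2 plans linear models with baseline for PRO scores. No input to the size of the loss is in the documents.

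Much of this stands. It limits the point to precision on a supportive endpoint, and any size is conditional on assumptions. It does not remove the point. The table's stated aim is superiority, and a shift table does not give an adjusted treatment difference. The Section 4.1.1 clause commits to nothing for PGIS, and the Section 4.7.2 sentence concerns scores and their change, not a yes/no improvement.

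A reader might infer three stronger things that the documents do not support.
- **That baseline category goes unused.** The shift analysis and shift tables use it descriptively.
- **That the SAP counts participants at the best category as non-improvers.** That is the literal reading of a percentage of participants, but no denominator is stated.
- **That these participants should be excluded**, by analogy with the PHQ-9 rule in Section 4.6.3.9.1 ("includes participants in the none, mild, moderate, or moderately severe category during baseline and with at least 1 postbaseline measurement"). That rule belongs to a safety analysis of worsening. The whole-population proportion is a legitimate estimand. Keeping everyone multiplies the risk difference by (1 − f) but leaves the risk ratio unchanged, and it biases neither arm.

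**Conclusion.** The point holds as a missing baseline-adjusted comparison. An unadjusted comparison of the PGIS-OSA improvement proportions is valid but less precise than the collected data allow. If 10-30% start at the best category, improvement is more likely with greater baseline severity and about 80 per arm are analysed, adjustment brings the variance of the risk difference to roughly 0.7-0.9 of the unadjusted value and adds roughly 4-14 points of power. The gain would be smaller with no severity gradient and few at the best category, and larger with a steep gradient. The direction is the same in every case examined; the size cannot be derived from the documents. No primary or type 1 error controlled conclusion is affected, so this is a minor improvement.

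**What to change.** In the PGIS row of Table GPIF.4.3, state that arms are compared among all analysed participants with an analysis adjusted for baseline PGIS category. Two options fit the existing plan:
- the logistic model of Section 4.4.1.1 (treatment, region, AHI stratum, gender) plus baseline PGIS category, reported with the unconditional risk difference already planned for the key secondary responders; or
- a CMH analysis stratified by baseline category.

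Name the CMH analysis in advance for the case of separation. The best category has no improvers in either arm by definition, so its coefficient has no finite estimate if category enters as a class effect. In CMH that stratum simply contributes nothing.

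For snoring, specify the 4-point item. Keep the planned shift table for everyone. The proportion among participants not at the best category at baseline may be added as a supplementary summary, labelled as describing that subset.

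The cost is a change to one table cell and reuse of a model already in the SAP. No new data are needed. It should be settled before unblinding, so that neither the denominator nor the model is chosen with results in view.

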4.4.3.1. Hierarchical Assessment of PRO Change

The analysis of the hierarchical composite endpoint will be performed with the Finkelstein-Schoenfeld method, and the win ratio (Pocock et al. 2012) will be reported as the measure of treatment effect. The population level summary of win ratio will be calculated as number of pairs of tirzepatide-treated participant “wins” divided by number of pairs of placebo-treated participant “wins.”

The Finkelstein-Schoenfeld method is based on the principle that each tirzepatide-treated participant is compared with every other placebo-treated participant in a pairwise manner that proceeds in a hierarchical fashion. Differences will be calculated as tirzepatide participant value minus placebo participant value. Each pairwise comparison will proceed in the following order and a winner has:

- Stage 1: For the change from baseline at Week 52 PROMIS Sleep-related impairment score:
 - A comparison is a win when the treatment difference is ≤ -4.9
 - A comparison is a loss when the treatment difference is ≥ 4.9
 - All other cases are a tie and the comparison of PROMIS Sleep disturbance score will be conducted (that is, proceed to Stage 2).
- Stage 2: For the change from baseline at Week 52 PROMIS Sleep disturbance score:
 - A comparison is a win when the treatment difference is ≤ -3.1 .
 - A comparison is a loss when the treatment difference is ≥ 3.1 .
 - In all other cases, the pair will be recorded as a tie.

Based on Donovan et al. (2020), a clinically important response of PROMIS sleep-related impairment for OSA participants is 4.9, and a clinically important response of PROMIS sleep disturbance for OSA participants is 3.1. Participants in this study had a mean BMI of 33.7 kg/m^2 , and one-half of them had moderate to severe OSA. Thus, the meaningful change threshold can be generalized to participants in the tirzepatide OSA trial.

For treatment policy estimand, missing values at Week 52 will be imputed through multiple imputations based on the reason of missingness with details described in Section [4.1.2](#).

For PRO measures, missing baseline values will be assumed to be missing at random and may be imputed through multiple imputation methods.

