**Figure GPIF.2.1****Graphical testing scheme for Study GPIF.**

3. Analysis Sets

Table GPIF.3.1 describes the populations that will be used for statistical analyses within each ISA of the master protocol. Additional intervention-specific populations for analyses may be described in the respective ISA.

Table GPIF.3.1. Description of Analysis Population

| Analysis Population | Description |
|---------------------------------|---|
| Entered | All participants who sign informed consent. |
| Randomized | All participants who are randomly assigned a study treatment (double-blind). |
| Modified intent-to-treat (mITT) | All randomized participants who are exposed to at least 1 dose of study intervention. |

Table GPIF.3.2. Description of Analysis Data Point Sets

| Analysis Set | Description |
|-----------------------------|---|
| Full analysis set (FAS) | Data obtained during treatment period of set of participants from the mITT population, regardless of adherence to study intervention. |
| Efficacy analysis set (EAS) | Data obtained during treatment period of set of participants from the mITT population, excluding data after discontinuation of study intervention (last dose + 7 days) and for ISA1, excluding data after initiating PAP therapy. |
| Safety analysis set (SS) | Data obtained during treatment and safety follow-up period of set of participants from the mITT population, regardless of adherence to study intervention. |

Abbreviations: EAS = efficacy analysis set; FAS = full analysis set; ISA = intervention-specific appendix; mITT = modified intent-to-treat; PAP = positive airway pressure; SS = safety analysis set.

4. Statistical Analyses

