4.1.2. Handling of Dropouts or Missing Data

For the primary and key secondary efficacy endpoint analyses aligned to the treatment regimen estimand and subject to Type 1 error rate control, missing data will be imputed based on the reason for the missing values, as described in [Table GPIF.4.2](#). For analyses aligned to the “efficacy” estimand, missing data will be considered missing at random and hence no explicit imputation will be performed.

For exploratory endpoints and safety analyses, missing values will not be explicitly imputed unless specified otherwise.

For analyses aligned to the treatment regimen estimand, the statistical inference over multiple imputations will be guided by the method proposed by Rubin (1987). The missing values will be handled as follows:

Table GPIF.4.2. Imputation Approaches to Handle Missing/Invalid Data for Treatment Regimen Estimand

| Missing/Invalid Data | Strategy to Handle Missing/Invalid Data | Assumptions for Missing Values | Methods to Handle Missing Values |
|--|---|--------------------------------|--|
| Data missing at baseline, invalid data collected or missing data after treatment DC due to the COVID-19 pandemic (after other reasons for missing data are ruled out), technical issues (that is, sensor error on PSG) leading to invalid measurements ascertained while on treatment, or missing data after study DC due to inadvertent enrollment. | Hypothetical | MAR | Multiple imputation assuming MAR |
| Missing data due to any other reason (for example, study DC due to any reason other than COVID-19 or inadvertent enrollment). | Treatment policy | MNAR | Retrieved dropout imputation ^a . If there are not enough retrieved dropouts to provide a reliable imputation model, placebo-based multiple imputation will be used. |

Abbreviations: COVID-19 = coronavirus disease-2019; DC = discontinuation; MAR = missing at random;

MNAR = missing not at random; PSG = polysomnography; SBP = systolic blood pressure.

^a Retrieved dropout imputation utilizes observed data from participants in the same treatment group who had outcome measures at Week 52 (or Week 48 for SBP) after early DC of study drug to impute the missing value.

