4.9. Changes to Protocol-Planned Analyses

Refer to [Table GPIF.1.1](#).

5. Sample Size Determination

Approximately 206 participants per ISA will be randomly assigned to either tirzepatide or placebo in a 1:1 ratio (approximately 103 participants per treatment arm), and the statistical power will be evaluated for the primary efficacy endpoint and key secondary combination PRO endpoint at a 2-sided significance level of 0.05. This sample size will provide the following:

- at least 90% power to demonstrate superiority of tirzepatide at the MTD (10 mg or 15 mg) to placebo for the mean percent change from baseline in AHI, assuming 50% improvement, with a common standard deviation of 50% and a dropout rate of 25%, and
- at least 90% power to demonstrate superiority of tirzepatide at the MTD (10 mg or 15 mg) to placebo for the hierarchical combination PRO endpoint using the Finkelstein-Schoenfeld method (Finkelstein and Schoenfeld 1999), with a dropout rate of 25%.

An upper limit of approximately 70% enrollment of male participants will be used to ensure a sufficiently large sample of female participants.

6. Supporting Documentation

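### Under its default efficacy estimand the hierarchical PROMIS win ratio has no workable rule for a missing Week 52 score, so the analysis reduces to completers; imputing from earlier visits would fix this cheaply.

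*SAP*

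**What the plan says.** SAP 4.4.3 sets a default for the supportive secondary endpoints: unless something else is specified, they follow the efficacy estimand, and the analysis "will be conducted using the EAS. Missing data will be handled using an MMRM". The hierarchical PROMIS endpoint stands in Table GPIF.4.3, headed "Secondary Measures Not Controlled for Type 1 Error", which refers it to SAP 4.4.3.1.

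Table GPIF.3.2 in SAP Section 3 defines the EAS as treatment-period data from the mITT population, "excluding data after discontinuation of study intervention (last dose + 7 days) and for ISA1, excluding data after initiating PAP therapy". A Week 52 score that was actually collected can therefore be removed. For the efficacy estimand SAP 4.1.2 adds that "missing data will be considered missing at random and hence no explicit imputation will be performed".

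SAP 4.4.3.1 compares each tirzepatide participant with each placebo participant on change to Week 52. Stage 1 uses sleep-related impairment with a margin of 4.9 points. Pairs not decided there go to Stage 2, sleep disturbance, with a margin of 3.1 points. Stage 2 closes with "In all other cases, the pair will be recorded as a tie". The same section says "For treatment policy estimand, missing values at Week 52 will be imputed through multiple imputations based on the reason of missingness", with details in SAP 4.1.2, and allows imputation of missing baseline PRO values. It gives no Week 52 rule for the efficacy estimand.

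**The concern.** An MMRM estimates arm means from incomplete longitudinal data. As planned here it produces no individual Week 52 scores, and a Finkelstein-Schoenfeld comparison can use nothing else. With explicit imputation also ruled out, a participant without an on-treatment Week 52 score (or, in ISA1, one who has started PAP) contributes no usable comparison. Stage 2 does not rescue the pair, because both PROMIS forms are scheduled at the same visits.

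The plan therefore states a missing-at-random assumption that this analysis does not deliver. ESS, FOSQ and SF-36v2 in the same table get an MMRM that draws on earlier visits. The schedule of activities (protocol 1.3) also collects PROMIS at Weeks 4, 12 and 20, but those scores go unused here. At stake is the interpretation of a supportive treatment effect: it would describe those who stayed on treatment rather than the hypothetical on-treatment effect defined in SAP 1.1.1.

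**Working it through.** **The plan's own figures.** SAP Section 5 gives about 103 per arm, 25% dropout and at least 90% power. For percent change in AHI, 103 × 0.75 = 77 completers per arm; with a difference of 50 and an SD of 50, two-sided 0.05, power is 99.999%, so that statement holds. The power statement for the combination PRO endpoint rests on the FOSQ assumptions in protocol 9.5. The documents give no SD, effect, tie share or power for the PROMIS hierarchy.

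**Incomplete pairs.** If a fraction *d* of each arm lacks a usable Week 52 score, the share of pairs with at least one member missing is 1 - (1 - *d*)².

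| *d* per arm | Incomplete pairs |
|---|---|
| 5% | 9.8% |
| 10% | 19.0% |
| 15% | 27.8% |
| 20% | 36.0% |
| 25% | 43.8% |
| 30% | 51.0% |

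With whole participants at 25%, 1 - (77 × 77)/(103 × 103) = 1 - 5929/10609 = 44.1%.

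**Tie or drop.** The win ratio is wins divided by losses. A pair scored as a tie enters neither count, and neither does a dropped pair, so both readings give the same completers-only ratio. Only the tie share differs. With assumed SD 6-10, correlation between forms 0.3-0.8 and a 3-point difference, within-margin ties are about 5-17% of complete pairs. Counting incomplete pairs as ties as well brings the total to about 46-54%.

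**Bias.** All inputs here are assumptions: 103 per arm, SD 8-10, 3-point difference, visit correlation 0.5-0.7, 25% dropout where not otherwise stated, and dropout log-odds slopes of 1 or 2 per SD of Week 20 response.

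| Dropout | Full-data win ratio | Completers-only |
|---|---|---|
| Random in both arms | - | No bias |
| Poor response, same mechanism in both arms | 1.45-1.65 | 1.46-1.70 |
| Random on tirzepatide, poor response on placebo, slope 1 | 1.46-1.65 | 1.25-1.45 |
| Same, slope 2 | 1.46-1.65 | 1.16-1.39 |
| Rates or mechanisms differing by arm, either direction | about 1.45-1.7 | about 1.2-2.0 |

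In the placebo-driven scenarios, MAR imputation from Week 20 returns 1.44-1.65. That is expected, since the simulated dropout depends only on observed scores.

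**The case against.** **SAP 4.4.3.1 already has a rule.** The default in 4.4.3 yields to anything specified elsewhere, the table sends the reader to 4.4.3.1, and that section imputes missing Week 52 values. A reader might infer from the gap that the SAP has no usable rule at all; the documents do not support that. For a treatment policy version there is one, and after it no pair is incomplete. What stands is that the rule is tied to that version alone. Its name differs from the treatment regimen estimand defined in SAP 1.1.1. SAP 4.1.2, to which it refers, limits its imputation to primary and key secondary endpoints, and pooling of the pairwise statistic is not described. It does not cover the efficacy estimand.

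**Missing is not a tie.** A reader might also infer that 44% of pairs will be recorded as ties. The stage rules classify a difference, an incomplete pair has none, and the SAP never scores it. The 44% is a share of incomplete pairs and depends on a planning dropout of 25%. Protocol 7.2 expects study discontinuation to be uncommon. Against that, the EAS also removes Week 52 data from people still in the study, so missingness can exceed study dropout.

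**Response-related dropout need not bias the ratio.** This is right: an equal mechanism in both arms leaves it almost unchanged. Nor do the documents say that dropout will differ by arm, or in which direction.

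**The consequences are small.** Also right. Both PROMIS scores have their own continuous analyses, with an MMRM for the efficacy estimand (SAP 4.4.1.1).

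**Conclusion.** The point holds for the efficacy estimand only. There, the stated method cannot supply the values that the comparison needs, and the analysis as written is completers-only. About 44% of pairs would be incomplete at 25% loss per arm and 19% at 10%. These shares follow from arithmetic once the loss rate is assumed.

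The possible bias, from a win ratio of about 1.45-1.7 to about 1.2-2.0, is illustrative. It rests on assumed SDs, correlations, effect and dropout mechanisms, and it arises only when dropout rate or mechanism differs by arm. It can favour either arm. Even under random dropout, imputation is somewhat more precise. The endpoint is other secondary and outside Type 1 error control, so this is a low-priority improvement that does not touch the primary or multiplicity-controlled conclusions.

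**What to change.** In SAP 4.4.3.1, as a stated exception to the no-imputation rule of 4.1.2:

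- For the efficacy estimand, multiply impute Week 52 PROMIS scores that are missing or excluded by the EAS. Impute under MAR, within arm, from baseline and the Week 4, 12 and 20 scores.
- Compute the Finkelstein-Schoenfeld statistic and the log win ratio in each imputed data set and pool them by Rubin's rules.
- Apply the tie rule only to pairs in which both values are available.
- Keep the existing treatment policy imputation analysis, call it by the defined name (treatment regimen), and state that SAP 4.1.2 applies to it.

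The cost is SAP wording and one imputation program, with no new data. The downside is reliance on an imputation model.
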